### **6.4. Drug Accountability, Dispensing and Destruction**

The Investigator is responsible for maintaining accurate accountability records of the IMP throughout the clinical trial.

Each administration of the IMP will be documented in the CRF.

The Investigator is responsible for returning all unused or partially used IMP to the Sponsor or overseeing the destruction of unused IMP. The IMP return or destruction will only occur after the drug accountability has been performed, and any discrepancies there may have been resolved by the Clinical Units.

### **6.5. Patient Identification**

At the Screening, each patient will be identified using a unique Identification Number.

Each patient will receive a Patient ID on Day 1 (of the Treatment Period) after eligibility for the clinical trial has been confirmed. The first two letters will correspond to the country where the Clinical Unit is located, the next two/three digits will correspond to the Clinical Unit and the last two/three digits will correspond to the patient.

Patients who withdraw or are withdrawn from clinical trial participation for any reason, regardless of whether IMP was administered or not, will retain their Patient ID and the patient will not be allowed to re-enter the clinical trial.

## 6.6. Administration of Investigational Medicinal Products

The IMP administration will consist of a single IV dose of SNF472 over a minimum of 2.5 and a maximum of 4-hour period during the patient's dialysis session. A minimum of 2.5 h of infusion is required.

The exact infusion starting and stopping times will be recorded in the CRF.

The appropriate volume of the investigational product will be administered as a constant rate IV infusion using a 100 mL bag of saline connected directly to the dialysis machine via an IV giving set, but always BEFORE the dialysis filter. The constant rate IV infusion will be carried out using an infusion pump for saline bags. SNF472 should NOT be administered directly intravenously.

The type of dialysis machine used will be documented in the CRF. The method of administration will be as follows:

[figure not shown]

Figure 2 Cartoon of the method of administration including the dialysis machine.

Any dosage interruptions will be recorded in the CRF (i.e., infusion stop and start times). In case there is an interruption of the infusion, once the infusion is re-started, the aim should be to deliver the whole dose, even if this takes longer than originally planned.

## **6.7. Compliance**

The Principal Investigator or designees will administer/oversee the administration of all IMPs. In addition, the following measures will be taken to ensure treatment compliance:

- The Investigator will attempt to enrol subjects able to understand and comply with the clinical trial
- The exact day and the starting and stopping IMP infusion times will be recorded in the CRF
- The Investigator will maintain accountability records showing the quantities of IMPs received at the Clinical Unit and dispensed to each patient

Any unused IMP, including empty, or partially used containers will be accounted for and returned to the manufacturing site for destruction after obtaining written Sponsor approval.

## **6.8. Concomitant Medications**

### **6.8.1. Prior and Concomitant Medication**

Any medicinal products, prescribed, or OTC taken by a patient other than the IMPs, are considered concomitant medication.

At screening, the patients' medical history and drug history will be recorded in the CRF under the medical history and treatment history sections. The drug history of the patient will include all medications taken in the last 6 months prior to study start. After screening, all medication (along with their daily dosage, duration, and reasons for administration) taken by patients will be recorded in the CRF under the concomitant medication section.

At each subsequent clinical trial visit, patients will be asked about what concomitant medications they have taken since the last visit. Any changes in the dose or dosing regimen of the concomitant medication must be recorded in the CRF.

## 7. VARIABLES AND METHODS OF ASSESSMENT

Refer to Table 1 for information regarding when each assessment will be performed.

For this clinical trial, a paper CRF will be utilised for data collection at the clinical sites. [REDACTED]

At baseline and for inclusion criterion purposes, several pictures of the main wound can be taken and emailed to the study PI so that he can decide which one is the one to be designated as “the” main wound. In following visits, the same wound has to be imaged so that the course of the wound can be assessed.

Image analysis software will be used. Each patient will have a personalised colour reference card with a unique barcode. This card should be placed next to the skin lesion before the image is taken, so that all wound images can be normalised in geometry, colour, and contrast in order to support quantitative measurements. The pictures of the wounds, primary, secondary, and tertiary, will be transferred to the database where they can be easily linked to their corresponding visit.

### 7.1. Safety Variables

#### 7.1.1. Medical History, Demographic, and Anthropometric Information

The medical history comprises:

- Previous illnesses and surgical procedures
- Family history
- History of drug and alcohol abuse

The treatment history will include all medication the patient has taken or is currently taking up until the Screening visit.

The following demographic and anthropometric information will be recorded at the Screening Visit:

- Age
- Sex
- Race (Caucasian, Hispanic, African-American, Asian or other)
- Ethnicity (Latino or Hispanic, non-Latino or non-Hispanic)
- Body weight (dry weight), without shoes (kg) (if without shoes is not possible then same conditions at each body weight measurement)

## 7.1.2. Adverse Events

### 7.1.2.1. Management of Adverse Events

The Investigator will carefully monitor each patient for AEs. In addition, the information on AEs will be obtained by regular questioning of each patient by the clinical trial staff. No leading questions should be asked. When an AE occurs, the Investigator will decide whether to withdraw the patient from the clinical trial and/or initiate appropriate treatment.

In the case of any event requiring medical intervention occurring during the Treatment Period, the Investigator will institute general supportive measures including, where necessary, respiratory assistance and cardiopulmonary resuscitation.

### 7.1.2.2. Definitions

An adverse event (AE) is any unfavourable and unintended sign, symptom, or disease that appears or worsens in a subject or clinical investigation subject during the period of observation in a clinical study.

The adverse event may be any of the following:

- A new illness,
- An exacerbation of a sign or symptom of the underlying condition under treatment or of a concomitant illness (including abnormal laboratory finding)
- Unrelated to participation in the clinical study or an effect of the study medication or comparator drug, or
- A combination of one or more of the above factors.

No causal relationship with the study medication is implied by the use of the term “adverse event.” An exacerbation of a pre-existing condition/illness is defined as a more frequent occurrence or as an increase in the severity of the pre-existing condition/illness during the study. Planned or elective surgical or invasive procedures for pre-existing conditions that have not worsened are not adverse events. However, any complication that occurs during a planned or elective surgery is an adverse event. (If the event fits the seriousness criteria, such as an extended hospitalisation, it will be considered a serious adverse event.) Conditions leading to unplanned surgical procedures may be adverse events.

In order for the Sponsor to collect additional information about the clinically important laboratory or diagnostic tests (eg, blood, urinalysis, ECG, imaging) abnormalities, at a minimum, the following abnormalities should be captured on the AE CRF:

- Any test result that meets the criteria for a SAE
- Any test abnormality that suggests a disease and/or organ toxicity that is new or has significantly worsened
- Any test abnormality that required the subject to have study medication discontinued or interrupted

- Any test abnormality that required the subject to receive specific corrective therapy, close observation, more frequent follow-up assessment, or further diagnostic investigation

Laboratory test abnormalities may not be of clinical significance in the absence of:

- Clinical symptoms
- Change in lifestyle
- Need for intervention

Only clinically significant test abnormalities should be reported as AEs. Determination of the clinical significance of test abnormalities is the responsibility of the Investigator. In particular, Grade 1 or 2 haematology, chemistry, abnormalities should be carefully considered for clinical relevance by the Investigator, as they are less likely to be of clinical significance as compared to Grade 3 or Grade 4 abnormalities. Haematology and chemistry abnormalities determined to be clinically relevant will be assigned a severity rating by the Investigator. A clinical diagnosis, rather than the changes in laboratory or other assessment should be recorded on the CRF as appropriate (eg, anaemia versus low haemoglobin value, bundle branch block rather than abnormal ECG).

All AEs, including intercurrent illnesses, occurring during the clinical trial will be documented in the CRF. Concomitant illnesses that existed prior to entry into the clinical trial will not be considered AEs unless they worsen during the Treatment Period. Pre-existing conditions will be recorded in the CRF on the Medical History or appropriate page.

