	SCR	TREATMENT PERIOD																														FU						
Week	-2, -1	1			2			3			4			5			6			7			8			9			10			11			12			13
Day		1	3	5	1	3	5	1	3	5	1	3	5	1	3	5	1	3	5	1	3	5	1	3	5	1	3	5	1	3	5	1	3	5	1	3	5	
Treatment History (prior medication) 	X																																					
Medical History	X																																					
Eligibility 	X																																					
CUA Diagnosis	X																																					
Treatment (Intravenous SNF472) 		X	X	X	X	X	X	X	X	X	X	X	X	X	X	X	X	X	X	X	X	X	X	X	X	X	X	X	X	X	X	X	X	X	X	X	X	
Wound QoL Score		X															X																				X	
Pain Score (VAS scale)	X	X			X						X						X						X													X	X	
Lesion Score (BJWAT)		X			X						X						X						X														X	X
Biomarkers		X																																				X
Plasma PK and PD sampling (predose & end of infusion)*		X																																			X	X

 Prior medication includes medications within 6 months of study start

 The inclusion/exclusion criteria will be assessed for each patient at Screening – final entry into the study depends on confirmation by the PI, [name]

 A Treatment Period includes 3 dialysis sessions/week x 12 weeks (36 treatments)

	SCR	TREATMENT PERIOD																														FU									
Week	-2, -1	1			2			3			4			5			6			7			8			9			10			11			12			13			
Day		1	3	5	1	3	5	1	3	5	1	3	5	1	3	5	1	3	5	1	3	5	1	3	5	1	3	5	1	3	5	1	3	5	1	3	5				
Concomitant Medication		X	X	X	X	X	X	X	X	X	X	X	X	X	X	X	X	X	X	X	X	X	X	X	X	X	X	X	X	X	X	X	X	X	X	X	X	X			
Adverse Events		X	X	X	X	X	X	X	X	X	X	X	X	X	X	X	X	X	X	X	X	X	X	X	X	X	X	X	X	X	X	X	X	X	X	X	X	X			
End of Study Visit																																									X

[figure not shown]
[figure not shown]

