#### **7.1.2.4. Recording of Adverse Events**

Adverse events will be collected from the time a patient signs the ICF until the Follow-up Visit.

All AEs, regardless of the relationship to IMP, must be recorded in the source documents (e.g., medical record) and will be recorded on the appropriate CRF pages, and documents provided by the Sponsor.

All AE reports should contain a brief description of the event, date, and time of onset, date and time of resolution, intensity, treatment required, relationship to IMP, action taken with the IMP, outcome, and whether the event is classified as serious.

Serious adverse events should be collected for up to 30 days after the last dose of the IMP for subjects unless the subject has withdrawn consent. This could be collected as a phone call.

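### Protocol 7.1.2.2 counts a worsening comorbidity as an AE only during the Treatment Period, which contradicts the wider AE and SAE windows in 7.1.2.2 and 7.1.2.4; hospitalisations are most exposed

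*Protocol*

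**What the plan says.** Protocol 7.1.2.2 contains two rules for the same kind of event. The general definition makes an AE any unfavourable sign, symptom or disease that "appears or worsens in a subject or clinical investigation subject during the period of observation in a clinical study". It lists as one type "An exacerbation of a sign or symptom of the underlying condition under treatment or of a concomitant illness", and it describes exacerbation as a more frequent occurrence or an "increase in the severity of the pre-existing condition/illness during the study". Later in the same section comes the narrower rule: "Concomitant illnesses that existed prior to entry into the clinical trial will not be considered AEs unless they worsen during the Treatment Period".

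A footnote to Table 1 fixes what the Treatment Period is: "A Treatment Period includes 3 dialysis sessions/week x 12 weeks (36 treatments"). Screening and the Week 13 Follow-up are separate columns of that table.

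Section 7.1.2.4 sets the collection windows. For AEs: "Adverse events will be collected from the time a patient signs the ICF until the Follow-up Visit". For serious events: "Serious adverse events should be collected for up to 30 days after the last dose of the IMP". Section 7.1.2.5 then places SAE reporting between the first administration and the Follow-up Visit.

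In the SAP, Section 9.2.3 identifies hospitalisations from AEs whose seriousness is recorded as requiring or prolonging hospitalisation. It identifies deaths from the AE list, or from the End of Study CRF when death is the primary reason for premature termination.

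**The concern.** A comorbidity such as heart failure that deteriorates after the last infusion is an AE under the general definition and under Section 7.1.2.4, but not under the concomitant-illness sentence. The same holds for deterioration between consent and first dose. That sentence is the most specific rule on when a pre-existing illness is not an AE, so a site could reasonably treat it as the governing one.

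Such events are foreseeable. All patients are on maintenance haemodialysis, and SAP 9.1.5 tabulates heart disease, vascular disease and diabetes in the medical history. Some of the AE list also feeds endpoints. Hospitalisation is a secondary endpoint (Protocol 4.2.2, SAP 5.2.2) and SAP 9.2.3 gives it no source other than the AE list. An admission that a site judges not to be an AE would drop out of both the safety tables and that endpoint.

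**Working it through.** The plan gives no figure to reproduce. The check is a comparison of windows, followed by day arithmetic and a rough sizing.

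**Windows side by side**

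| Place in Protocol | Governs | Start | End |
|---|---|---|---|
| 7.1.2.2, concomitant-illness sentence | Worsening of a concomitant illness | Start of Treatment Period | End of Treatment Period (Week 12) |
| 7.1.2.2, AE definition | Any AE | Period of observation | Period of observation |
| 7.1.2.2, exacerbation | Pre-existing condition or illness | During the study | During the study |
| 7.1.2.4 | AE collection | Signed ICF | Follow-up Visit |
| 7.1.2.4 | SAE collection | No separate start given | 30 days after last dose |
| 7.1.2.5 | SAE reporting | First administration | Follow-up Visit |

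The first row is narrower than the collection windows at both ends. Section 7.1.2.5 describes the period of observation as first dose to Follow-up. Even if that meaning is carried back into the AE definition, the conflict after the last infusion remains. The last two rows also disagree with each other on when SAEs stop.

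**Days affected**

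- Last planned infusion, Week 12 Day 5: 11 × 7 + 5 = study day 82.
- Week 13 runs from 12 × 7 + 1 = day 85 to 13 × 7 = day 91.
- Last infusion to Follow-up: 85 − 82 = 3 to 91 − 82 = 9 days. This is the AE gap.
- Last dose + 30 days: 82 + 30 = day 112. This is the end of the SAE gap.
- Part of the SAE gap after the Follow-up Visit: 112 − 91 = 21 to 112 − 85 = 27 days.
- If the Treatment Period is read as ending on day 84 (12 × 7), the AE gap is 1 to 7 days and the SAE gap 28 days.
- Before first dose: up to 14 days of screening (Section 8.2.1).

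**A ceiling on deaths in the SAE gap**

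Inputs: one-year survival S = 0.45 (Protocol 2.2) or 0.50 (Protocol 4.3, one-year mortality about 50%), and 15 patients (Protocol 5.1). Constant hazard is an assumption. Risk over d days = 1 − S^(d/365).

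- S = 0.45, d = 30: 1 − 0.45^(30/365) = 0.0635. Among 15 completers: 15 × 0.0635 = 0.95 expected deaths.
- S = 0.50, d = 30: 0.0554, so 15 × 0.0554 = 0.83.
- If 15 patients start and are depleted over 12 weeks at S = 0.45: weekly hazard = −ln(0.45)/52 = 0.01536; survival to Week 12 = exp(−12 × 0.01536) = 0.832; 15 × 0.832 × (1 − exp(−0.01536 × 30/7)) = 0.79.
- S = 0.45, only the 21 to 27 days after Follow-up: risks 0.0449 and 0.0574, so 0.67 to 0.86 among 15 completers.

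The Protocol defines the 15 as patients who complete 12 weeks, so 0.95 fits its target and 0.79 is the version that allows for attrition. Both are all-cause figures. The deaths that could be misfiled under the clause, namely those attributed to worsening of a concomitant illness, are a subset of unknown size.

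**The case against.** A reader might infer that post-treatment deaths fall out altogether, on the reasoning that what is not an AE cannot be an SAE. The documents do not support this. Section 7.1.2.3.1 defines an SAE as any untoward medical occurrence with a serious outcome, without reference to the Treatment Period, and Section 7.1.2.4 separately asks for SAEs to 30 days. Death is a secondary endpoint in its own right, SAP 9.2.3 has the End of Study CRF as a second source, and Section 5.5 allows a death-registry check for withdrawn patients.

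A reader might also infer that worsening of calciphylaxis itself is excluded. The clause speaks of concomitant illnesses, and the AE definition names the condition under treatment separately, so this is not clearly so. Nor do the documents show that most serious post-treatment events would be worsening of something pre-existing. Protocol 2.2 attributes over half of the mortality to infections, and a new infection is a new illness that the clause does not touch.

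Finally, several sentences point to the wider window, including the one just before the clause, which says all AEs during the trial are documented.

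Much of this stands, and it narrows the point. It does not remove it. Documenting all AEs does not help when the disputed sentence decides what counts as an AE. The SAE definition covers serious admissions as well as deaths, but a site still has two answers to choose from, and hospitalisations have no second source in the SAP. For deaths, the End of Study CRF route applies to premature termination and the registry check to withdrawals. Neither would be expected to catch a patient who completes Week 13 and dies before the 30 days are up.

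**Conclusion.** The contradiction is real and should be corrected. Read literally, the clause can leave out worsening of a comorbidity in up to 14 days before first dose, in about 3 to 9 days between last infusion and Follow-up for AEs, and in up to 30 days after the last dose for SAEs. Hospitalisations are affected most. For deaths, the residual risk is limited to one after the Week 13 visit and within 30 days of the last dose, attributed to a comorbidity and not reported under the SAE definition.

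The figure of about 0.8 to 0.95 deaths in 30 days among 15 patients is an all-cause upper bound for such deaths at 45% one-year survival and constant hazard. It is not an estimate of deaths lost. Exclusion criterion 4 (no reasonable expectation of survival beyond 6 months) would lower it; the excess mortality soon after diagnosis described in Protocol 2.2 would raise it. How many events would actually be missed depends on which sentence each site follows, which the documents do not settle. SAP 9.3.1 states no AE window, and SAP Section 8.5 was not available to check.

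**What to change.** In Protocol 7.1.2.2, replace the reference to the Treatment Period in the concomitant-illness sentence with: *during the applicable AE or SAE collection period (Section 7.1.2.4)*. The word applicable is needed because 7.1.2.4 holds two windows, one for AEs and one for SAEs. The change closes the gap before first dose as well as the one after the last infusion.

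Reconcile the SAE reporting window in Section 7.1.2.5 (first administration to Follow-up Visit) with the 30-day SAE collection in Section 7.1.2.4. Without this, serious events after Week 13 are collected under one section and fall outside the reporting period of the other.

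The cost is two sentences. No visit is added, since Section 7.1.2.4 already allows late SAEs to be gathered by telephone. A few more events may be recorded.

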### **7.1.2.3. Assessment of Adverse Events**

The Investigator will assess each AE according to the categories discussed in the sections below.

#### **7.1.2.3.1. Seriousness**

A SAE is defined as any untoward medical occurrence that at any dose:

- Results in death
- Is life-threatening; this means that the patient was at risk of death at the time of the event; it does not mean that the event hypothetically might have caused death if it were more severe
- Requires hospitalisation or prolongation in existing hospitalisation
- Results in persistent or significant disability or incapacity
- Is a congenital anomaly or a birth defect
- Is an important medical event that may not result in death, be life threatening, or require hospitalization, but may be considered an SAE when, based upon appropriate medical judgment, it may jeopardize the subject and may require medical or surgical intervention to prevent one of the outcomes listed in this definition

Examples of such events are invasive or malignant cancers, intensive treatment in an emergency room or at home for allergic bronchospasm, blood dyscrasias or convulsions that do not result in hospitalisation, or development of drug dependency or drug abuse.

Note that an AE or suspected adverse reaction is considered “life-threatening” for reporting as an SAE if, in the view of either the Investigator or the Sponsor, its occurrence places the subject at immediate risk of death. It does not include an AE or suspected adverse reaction that, had it occurred in a more severe form, might have caused death.

The following events do not meet the definition of an SAE with regard to hospitalization: planned hospitalization for a condition present prior to the subject’s enrolment in the study, hospitalization of the subject for compliance/convenience reasons, planned hospitalization for an elective medical/surgical procedure, scheduled treatments, or routine check-ups, or a hospitalization or an emergency room visit lasting less than 24 hours.

#### **7.1.2.3.2. Intensity**

The Investigator will assess the severity of AEs according to the following definitions:

- Grade 1 (Mild): asymptomatic or transient, short in duration (< 1 week), no change in lifestyle, and/or no medications required.
- Grade 2 (Moderate): symptomatic, duration (1 to 2 weeks), alters lifestyle occasionally, medication relieves symptoms (may be prescription), and/or study medication is continued.
- Grade 3 (Severe): prolonged symptoms, reversible, major functional impairment; prescription medications provide partial relief; may be hospitalized < 24 hours; temporary or permanent study medication discontinuation.
- Grade 4 (includes Life threatening): at risk of death; substantial disability, especially if permanent; hospitalized > 24 hours; permanent study medication discontinued.

